### 5.0 Specific aims

A. To determine the change in total sleep time as measured by polysomnography(PSG) in CLL patients with fatigue of  $\geq$  4(on a 0-10 scale) on the MD Anderson symptom inventory (MDASI) before and after the 1st cycle of treatment (day 57 +/- 3 days) with lenalidomide,

B.1. To summarize variables associated with sleep architecture as measured by PSG before and after the 1st cycle of treatment (57 days +/- 3 days) with lenalidomide, in this subset of population,

B.2. To summarize the variables associated with PSQI, Epworth sleep scale, actigraphy in relation to sleep and FACIT-F in relation to fatigue before and after treatment (57 days +/- 3 days) with lenalidomide.

B.3. To determine the relationship between changes in inflammatory cytokines levels and the frequency and intensity of fatigue and sleep disturbances in these patients as measured by the MDASI before and after the 1st cycle of treatment (57 days +/- 3 days) with lenalidomide.

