## 8.0 Treatment Plan

Twelve eligible patients with CLL will be recruited from the Leukemia Clinic at MDACC. Patients complete questionnaires - MD Anderson symptom inventory(MDASI) for cancer related symptoms and screening for eligibility, Pittsburg Sleep Quality Index (PSQI), Epworth sedation scale, for assessment of sleep, FACIT-F to evaluate fatigue and quality of life and performance status is measured by Zubrod performance status and anxiety depression - Hospital anxiety depression scale(HADS). The laboratory correlates will include baseline hemoglobin level, electrolytes, serum IL-1, IL-6, IL-8 and TNF-á, IL-10 and MIP-1. This assessment will be performed a day before the initiation of therapy. Repeat assessments will be done on day 29 (+/- 3 days), and Day 57 (+/- 3 days), and again prior to the initiation of the next treatment phase. The day 15 (+/- 3 days) and day 43 (+/- 3 days) symptoms assessments will be performed via telephone. During the treatment period patient will wear an actigraph on the wrist to monitor physical activity. The actigraph will be used to record and evaluate sleep quantity and quality, daytime activity levels. Patient will maintain a sleep and fatigue dairy during the course of the treatment from prior to Day 1 to prior to the next treatment phase (at least 2 days). Patient will undergo polysomnography (PSG) to evaluate sleep pattern prior to Day 1 (after initial oncological visit) and prior to the next treatment phase (Day 57 (+/- 3 days)), at least 2 days prior to the initiation of treatment).

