h) **Polysomnography** (PSG) is considered the "gold standard" for the objective measurement of sleep parameters. Recoding details are as follows. PSG is recommended or essential in the study of sleep disorders such as insomnia in determining Total sleep time, SOL, NWAK, WASO, SE, Apnea Hypopnea Index, PLMAI (Periodic Limb Movement Arousal Index), arousals and stages of sleep (sleep architecture)(30). PSG will be performed at the UT MDACC Sleep Center (directed by [name], co-Investigator) by a registered polysomnographic technologist. A sleep variable will be obtained using 12-channel polysomnography (Nihon Kohden, Foothills Ranch, CA). The twelve channels of data will include: central and occipital electroencephalogram, bilateral electrooculogram, submental electromyogram, thoracic and abdominal respiratory effort, airflow, electrocardiogram, tibialis electromyogram, and oximetry. Sleep record will be scored by registered polysomnographic technologists according to the standard criteria of Rechtschaffen and Kales. Records will be scored for total sleep time, number of minutes of wake after sleep onset (WASO), number of awakenings, sleep latency, sleep efficiency, and the percentages of stages 1,2,3,4, and REM sleep, as well as cortical arousals (defined as sudden increases in electroencephalogram frequency of at least 3 second duration, following at least 10 seconds of continuous sleep, with or without accompanying muscle activity). Study participation will involve 12 hours including arrival at the Sleep Center at approximately 8pm, completion of questionnaires, instrumentation with sensors, and completion of post sleep questionnaires. This assessment would be performed on prior to Day 1 and prior to the 2nd cycle (Day 57 (+/- 3 days)), at least 2 days prior to the initiation of treatment).

Laboratory evaluation: serum cytokines (IL-1, TNF-, IL-8, IL-10 and IL-6) at baseline before treatment, day 29 (+/- 3 days) and day 57 (+/- 3 days).

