**Cytokine Measures:** The serum samples will be stored frozen for subsequent batch analysis to construct a cytokine profile. The cytokine profile will be correlated with the degree of symptoms and for the responsiveness or failure to respond to lenalidomide therapy. Pro-inflammatory sleep inducing cytokines (IL-1, IL-6, IL-8 and TNF-á, IL-10 and MIP-1), anti-inflammatory anti-sleep inducing cytokine IL-10 will be measured in the serum of patients using the Multiplex Luminex Assay platform and commercially available cytokine-coated beads (Biosource Inc.). The Multiplex Bead Immunoassay will be used to measure serum/plasma levels of these cytokines and the assay sensitivity for these cytokines is 3-6 pg/mL. The Multiplex Bead immunoassay represents the development of a Multiplex Assay is designed to work in conjunction with the Luminex 100 analyzer (Luminex Corp., Austin, TX), associated software and fluorescently encoded microspheres. In this assay, each microsphere is labeled with a distinguishable fluorophore that allows it to be assigned or gated to a particular region by the scanner. Antibodies, specific for the cytokine or protein of interest (purchased from Biosource International, Camarillo, CA) are covalently linked to individually beads of a different fluorescent marker. When the beads are reacted with sera or plasma containing cytokines, the cytokines bind to the bead coated with the complementary antibody, and its unique fluorescent signature can detect cytokine-bead complex by the Luminex 100 analyzer. These assays have been performedinDr.[name]'slaboratory.

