# **10.0 Statistics**

The primary objective is to explore a change in total sleep time using Polysomnography (PSG) in CLL patients with fatigue of greator or equal to 4 (in a 0-10 scale) on the MD Anderson symptom inventory (MDASI) before and after the 1st cycle of treatment (57days) with a Lenalidomide. We will use a paired t test, a Wilcoxon rank sum test, or a sign test (depending on the distribution of the data) to determine changes in total sleep time before and after treatment (day 57). Prior studies have indicated a clinically significant change in the total sleep time estimated by PSG to be 20 min, using a pilot open labeled design we anticipate obtaining a similar outcome by accruing 12 patients (34). Due to the challenge of accrual, expense and time constraints, a relatively small sample size has been selected. Assuming we will enroll 12 evaluable patients, we will be able to declare as significant differences between pre and post that are 0.89 standard deviations or greater with 80% power and a two-sided significance level of 0.05. We will summarize variables associated with sleep (PSG, Actigraphy, PSQI, ESS), fatigue (FACIT- F, HADS, actigraphy) and serum cytokines (IL-1, IL-6, IL-8 and TNF-á, IL-10 and MIP-1). In addition we will correlate these variables with changes in sleep time, using Pearson or Spearman correlation coefficients, depending on the distribution of the data. In addition this study will obtain preliminary data to determine the effect size for a future larger randomized controlledtrial.

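### Does Section 10.0 leave aim B.3 (cytokine changes against MDASI fatigue and sleep disturbance) without an analysis?

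*Combined protocol and SAP*

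**What the plan says.** Section 5.0, aim B.3, sets the question: "To determine the relationship between changes in inflammatory cytokines levels and the frequency and intensity of fatigue and sleep disturbances in these patients". It names the instrument and the window: "as measured by the MDASI before and after the 1st cycle of treatment (57 days +/- 3 days".

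Section 10.0 has three analysis elements. The first is a before-and-after test of total sleep time on PSG. The second is descriptive: "We will summarize variables associated with sleep (PSG, Actigraphy, PSQI, ESS), fatigue (FACIT- F, HADS, actigraphy) and serum cytokines". The third is correlation: "In addition we will correlate these variables with changes in sleep time, using Pearson or Spearman correlation coefficients", with the choice of coefficient left to the distribution of the data. Section 10.0 names the MDASI once, to define the population by a fatigue score of at least 4.

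Outside Section 10.0, the Cytokine Measures text in Section 9.0 adds: "The cytokine profile will be correlated with the degree of symptoms and for the responsiveness or failure to respond to lenalidomide therapy". Data collection is in Sections 8.0 and 9.0. The MDASI belongs to the questionnaire battery ("Patients complete questionnaires - MD Anderson symptom inventory(MDASI) for cancer related symptoms and screening for eligibility"), and Section 8.0 goes on: "Repeat assessments will be done on day 29 (+/- 3 days), and Day 57 (+/- 3 days". The laboratory text ("Laboratory evaluation: serum cytokines (IL-1, TNF-, IL-8, IL-10 and IL-6) at baseline before treatment") continues with Day 29 and Day 57.

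**The concern.** Taken alone, Section 10.0 does not answer aim B.3. Its correlations have a different target, change in sleep time. Sleep time on PSG is not fatigue, and it is not the MDASI rating of disturbed sleep. Its fatigue variables are FACIT-F, HADS and actigraphy. Followed to the letter and in isolation, the section relates no cytokine to any fatigue score, and it does not say that cytokines enter as changes.

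The risk would be twofold. Aim B.3 might go unreported. Or it might be run with choices made after seeing the data: whether the MDASI enters as a change or as a Day 57 level, and whether Pearson or Spearman is used. With 12 patients and many cytokine-by-symptom pairs, such choices can alter which associations look notable. The link between cytokines and symptoms also matters to the study, because the Rationale (Section 3.0) rests on it.

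**Working it through.** **1. The plan's own figure.** Section 10.0 gives a detectable difference of 0.89 SD with 12 evaluable patients, 80% power and two-sided 0.05. For a paired t test the noncentrality is 0.89 x sqrt(12) = 3.08 on 11 degrees of freedom. This gives power of 80.1%, and the detectable difference at 80% power is 0.889 SD. The figure reproduces. It concerns total sleep time only and does not depend on how aim B.3 is handled.

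**2. What aim B.3 needs, and where the document gives it.**

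| Element | Where it is given |
|---|---|
| Cytokine side: changes in levels | Section 5.0, B.3 |
| Symptom side: fatigue and sleep disturbance | Section 5.0, B.3 |
| Instrument: MDASI | Section 5.0, B.3 |
| Window: before and after cycle 1, Day 57 +/- 3 | Section 5.0, B.3 |
| Type of analysis: correlation with symptoms | Section 9.0, Cytokine Measures |
| Coefficient: Pearson or Spearman, by distribution | Section 10.0 (stated there for sleep time) |
| Cytokine data at baseline and Day 57 | Sections 8.0 and 9.0 |
| MDASI data at baseline and Day 57 | Section 8.0 (repeat is an inference) and B.3 |

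The last row is an inference because Section 8.0 does not name the instruments to be repeated. The MDASI is, however, in the battery that precedes that statement, and B.3 itself requires it before and after treatment.

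**3. Number of correlations.** Assume change against change for two MDASI items, fatigue and disturbed sleep. The laboratory list in Section 9.0 has five cytokines: 5 x 2 = 10. The lists in Sections 8.0 and 10.0 add MIP-1: 6 x 2 = 12. Section 10.0 names none of these.

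**4. What these correlations can show with n = 12.**
- Critical Pearson value, two-sided 0.05: t(0.975, 10) = 2.228, so r = 2.228 / sqrt(10 + 2.228^2) = 0.576.
- 95% interval for an observed r of 0.5: tanh(0.549 +/- 1.96 / sqrt(9)) = -0.10 to 0.83.
- Power at a true r of 0.5, bivariate normal, 200,000 simulated samples: 0.40.
- Expected chance findings if every pair were tested at 0.05: 10 x 0.05 = 0.5, or 12 x 0.05 = 0.6.

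These figures describe any correlation in 12 patients. They are the same with or without an extra sentence in Section 10.0, so they do not measure the gap. They show that B.3 can yield only rough estimates.

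An exact Spearman threshold adds nothing useful. It can be computed for untied data (0.587), but MDASI items are 0-10 ratings. With whole-number ratings assumed, and normal changes of SD 1.5 to 5 rounded to integers, at most 1.2% of simulated samples of 12 were free of ties.

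**5. What stays open.** Two choices remain. On change or Day 57 level, B.3 pairs changes in cytokines with MDASI ratings before and after treatment, so change against change is the natural reading. On Pearson or Spearman, Section 10.0 already lets the distribution decide for its stated correlations, so B.3 would be no less determined than they are.

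**The case for a change.** The strongest case for acting is that the statistics section is where an analyst looks, and it does not contain B.3. The sentence in Section 9.0 shows intent, but it names no instrument, item, time point, change score or coefficient. The Pearson or Spearman clause grammatically covers only correlations with sleep time. Section 2.0 says the results will feed a larger randomised trial, so the reporting of a stated aim should not depend on the analyst joining up three sections. The remedy would cost one sentence and no new data.

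Part of this stands. Section 10.0 does not carry B.3 through, and the repeat MDASI at Day 57 has to be inferred. What does not stand is the consequence. For B.3 to be lost, an analyst would have to ignore the aims and Section 9.0 of a single short document. A sentence that kept the choice of coefficient open would remove none of the freedom complained of. Fixing the coefficient would help only slightly, in a set of 10 to 12 exploratory estimates with intervals as wide as those shown.

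Two side issues are clerical. Section 9.0's laboratory list omits MIP-1, which Sections 8.0 and 10.0 include. B.3 speaks of frequency as well as intensity, while Section 9.0 describes MDASI items as severity ratings. Neither alters a stated analysis.

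**Conclusion.** The observation is correct but calls for no change. Section 10.0 omits a sentence on B.3. The rest of the document supplies the variables, instrument, window and type of analysis, and Section 10.0 offers a usable rule for the coefficient. A competent analyst would arrive at the same 10 or 12 correlations that a fuller Section 10.0 would list. No stated rule or figure gives a wrong result, and the 0.89 SD figure for total sleep time reproduces.

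The size is small: a secondary aim of a 12-patient, single-arm pilot whose stated purpose is preliminary data. Each coefficient would carry an interval about as wide as -0.10 to 0.83 around 0.5, so the B.3 results should be read as exploratory estimates however the section is worded.

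The conclusion assumes change against change on two MDASI items, all 12 patients with both measures at both times, and an MDASI at Day 57, which is inferred from Section 8.0 and from B.3 itself.
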